The primary objective of this study is to determine the activity of lenalidomide in pediatric patients with relapsed/refractory AML (with second or greater relapse or refractory to at least 2 prior induction attempts). Treatment of an AML recurrence following allogeneic HSCT commonly includes a rapid taper of immune-suppression used for prophylaxis and/or treatment of acute GVHD. In this setting, mild GVHD is an expected and a desirable toxicity. The use of the immune-modulatory drug, lenalidomide, in patients at risk for acute GVHD will be challenging but with the potential for benefit to the patient with induction of mild but manageable GVHD. Accordingly, this study will attempt to keep patients with new mild GVHD on protocol therapy, while recognizing that Grade 3 or greater acute GVHD will be an unacceptable toxicity. First, patients with active GVHD or requiring immune-suppression including steroids for GVHD control are not eligible for enrollment. Patients with a history of Grade 3 or greater GVHD or those on therapeutic dosing of immune suppressive therapy will be discussed with the study chair prior to enrollment and require a longer observation time off immune-suppression prior to enrollment (4 weeks) compared to those without a history of severe GVHD or who are already on tapering dosing of immune suppressive therapy without signs of GVHD (2 weeks off immune-suppression) (see Sections 6.25, 7.2 and 8.2.1). Second, patients who develop Grade 3 or greater GVHD, or lower grade GVHD that does not respond to protocol prescribed interventions (Section 8.2.1) will be off study treatment. No dose reduction is planned as it is not clear that this toxicity would improve and be altered by dose adjustment. Incidence of GVHD will be closely monitored and the study will be closed to post-HSCT patients if stopping thresholds for Grade 3 or greater GVHD are crossed (see Section 10.9.1). Patients will be monitored for development of chronic GVHD.

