8.2. Treatment Administration and Schedule

Lenalidomide will be administered either in capsules containing 2.5 mg, 5 mg, 10 mg, 15 mg, 20 mg or 25 mg or as an oral suspension (10 mg/mL). The oral suspension is available for use in

subjects who are unable to swallow the capsules or at the discretion of the investigator. The starting dose of lenalidomide will be 2 mg/kg/day with a maximum dose of 70 mg/day. Lenalidomide will be administered orally once daily for the first 21 days of every 28-day cycle. Daily dosage should be administered using the combinations that yield the least amount of capsules. However, if a subject is unable to swallow big capsules, varying, appropriate strength combinations may be considered during medication assignment using the IWRS. The prescribed dose should be the closest dose that can be given to the calculated dose based on the strengths of lenalidomide available. If the calculated dose falls between two integers, the dose calculated should be rounded up or down to the nearest whole number. The actual dose to be administered can be determined after rounding the calculated dose. For dose reductions, the dose calculated should be to the nearest whole number. For a dosing table with guidelines reflecting this approach for the lenalidomide capsules, refer to [Appendix B](#).

Refer to [Appendix C](#) for dosing guidelines for the lenalidomide oral suspension.

After completion of 12 cycles of study treatment, if deemed necessary or useful by the Investigator and with approval of the Sponsor, subjects who demonstrate clinical benefit as per the Investigator from lenalidomide may continue to receive oral lenalidomide (either capsules or oral suspension) in an OEP until they meet the criteria for study discontinuation (see [Section 12](#)).

Dose interruptions/reductions will be permitted for episodes of myelosuppression, non-hematologic toxicities, and AEs. For additional details see [Section 8.2.1](#).

In the event of specific protocol-defined toxicity, no more than 2 dose reductions will be allowed to doses of 1.4 mg/kg/day (not exceeding 50 mg/day) and 1 mg/kg/day (not exceeding 35 mg/day) during the study. The dose will not be re-escalated once it has been reduced ([Table 6](#)). Subjects who do not tolerate the minimum dose level of 1 mg/kg/day (not exceeding 35 mg/day) will be discontinued from the study.

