8.2.1. Dose Reductions/Interruptions

Dose reduction guidelines are as follows:

- Two dose reductions will be allowed (Table 6) in the event of specific protocol-defined toxicity. If treatment is interrupted for toxicity as described below, lenalidomide will be resumed at dose level -1 once the toxicity has resolved to ≤ Grade 1. If toxicity recurs, lenalidomide will be interrupted and upon resolution, the subject will resume at dose level -2.
- The dose will not be re-escalated if the lower dose is tolerated.
- Subjects who do not tolerate 1 mg/kg/day (dose level -2) will discontinue lenalidomide administration.

Table 6: Dose Reductions of Lenalidomide

Dose Level	Dose
Starting dose	2.0 mg/kg/day (maximum dose of 70 mg/day for subjects ≥ 35 kg)
Dose Level -1	1.4 mg/kg/day (not exceeding 50 mg/day for subjects initially dosed at 70 mg/day)
Dose Level -2	1.0 mg/kg/day (not exceeding 35 mg/day for subjects initially dosed at 70 mg/day)

Definition of Toxicity Requiring Treatment Interruption and/or Dose De-escalation

Lenalidomide dosing will be interrupted for any of the following toxicities at least possibly attributed to lenalidomide:

- Any Grade 4 non-hematological toxicity *with the specific exclusion* of fever or infection.
- Any Grade 3 non-hematological toxicity *with the specific exclusion* of:
 - Grade 3 nausea and vomiting controlled by antiemetics.

- Grade 3 fever or infection.
- Grade 3 hypophosphatemia, hypokalemia, hypocalcemia or hypomagnesemia responsive to oral supplementation.
- Grade 3 TLS: With close monitoring per the [REDACTED] TLS monitoring guidelines ([Appendix M](#) Tumor Lysis Syndrome), lenalidomide dose may be continued uninterrupted provided continued treatment does not pose a safety concern in the presence of TLS event. If interrupted, lenalidomide treatment may be restarted at the same dose level after TLS is under control at the discretion of the Investigator.

NOTE: For purposes of grading AST and ALT adverse events in this study, the ULN for AST is 50 U/L and the ULN for ALT is 45 U/L.

Lenalidomide will be held for any subject experiencing hemorrhagic or bullous skin rash until a specific evaluation to exclude toxic epidermal necrolysis and/or Stevens-Johnson syndrome has been performed. Any subject with evidence of TEN or Stevens-Johnson syndrome will not be retreated with lenalidomide.

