Grade 3 ALT/AST values that return to levels that meet initial eligibility criteria within 7 days of IP interruption do not require a dose reduction. These subjects may resume treatment at the original dose level. If the toxicity recurs, then dose de-escalation is indicated.

Day 1 of Cycle 2 and beyond may be delayed up to 14 days from the end of the prior cycle in order for subjects to recover from toxicity. If a study interruption has lasted for more than 14 days, the Investigator should contact the Medical Monitor to discuss whether the subject should be continued on the study.

Special Instructions for Myelosuppression:

Due to the underlying marrow infiltrating malignancy, myelosuppression is universal and expected in patients with AML. Therefore, myelosuppression (anemia, neutropenia, and thrombocytopenia) will not require dose reduction or interruption *except* in the case of neutropenia or thrombocytopenia due to prolonged bone marrow aplasia at the end of a treatment cycle in subjects who have achieved remission.

- For subjects who have achieved remission:
 - Prolonged bone marrow aplasia is defined as lack of peripheral blood count recovery to $ANC \geq 500/mm^3$ and platelets $\geq 50,000/mL$ without transfusion for 7 days in the absence of leukemia (bone marrow biopsy demonstrate hypocellularity without evidence of leukemia) at Day 43 of a cycle (ie, failure to start the next cycle within 14 days).
 - The lenalidomide dose will be interrupted and the start of the next cycle will be delayed until count recovery.
 - Prolonged delay (ie, failure to start the next cycle within 14 days) for subjects in remission will require dose de-escalation.
 - If the peripheral blood counts recover within 14 days, the subject will proceed to the next cycle without dose reduction.

- If the peripheral blood counts do not recover within 14 days, repeat bone marrow evaluation including bone marrow biopsy every 7-14 days to assess cellularity and to evaluate for relapse/persistent leukemia.
- For subjects who have not achieved remission:
 - In general, subjects who have not achieved remission and have evidence of residual leukemia will proceed to the next cycle as scheduled regardless of count recovery.
- For subjects with residual leukemia:
 - If residual leukemia is demonstrated and the subject previously had achieved CR/CRi, the subject will be discontinued from the study.

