 - If residual leukemia is demonstrated, which is stable from prior assessments (ie, subject with previous PR/treatment failure), the subject will proceed to the next cycle of lenalidomide as scheduled without delay and without regard to peripheral blood counts. Lenalidomide dose will NOT be decreased.

Special Instructions for Management of Graft Versus Host Disease (GVHD):

Post-HSCT subjects will be monitored closely for development of GVHD of the skin, liver, or gut, see [Appendix K](#) for grading criteria.

- Subjects with Grade 1 or 2 GVHD (any site, biopsy proven or probable, ie, requires systemic steroid treatment) will be managed at the discretion of the local bone marrow transplant (BMT) physician and lenalidomide will be held.
 - If the acute GVHD resolves within 14 days and the subject is being treated with no more than topical therapies and/or up to 0.5 mg/kg/day corticosteroids (prednisone equivalents), lenalidomide will be restarted at the same prior dose.
 - After 14 days, subjects requiring more than 0.5 mg/kg/day corticosteroids or other systemic therapy (ie, not including topical therapies) to manage the acute GVHD will be discontinued from the study.
- Subjects with Grade 3 or 4 GVHD (any site, suspected or biopsy proven) will have lenalidomide discontinued permanently and will be managed at the discretion of the local HSCT physician. These subjects will be discontinued from the study.

Guidelines for Renal Insufficiency

- Lenalidomide is primarily excreted unchanged by the kidney; therefore, study treatment will be held for subjects who experience CLcr < 70 mL/min (confirmed by repeat creatinine measurement within 3 days). If CLcr returns to levels that meet initial eligibility criteria (> 70 mL/min) within 7 days of IP interruption, the subject may resume treatment at a full dose. However, if the subject improves within 14 days, a dose reduction by 1 dose level of study treatment will be considered at the discretion of the Investigator, and after careful consideration of the subject's renal impairment etiology and the subject's tolerability to lenalidomide. If toxicity does not resolve to eligibility by 14 days of dose interruption, then the subject will be off study treatment.

Dose Discontinuation:

- Subjects experiencing a thromboembolic event unrelated to a central line will be discontinued from lenalidomide treatment.

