- As described above, under dose interruption, any subject with evidence of TEN or Stevens-Johnson syndrome will not be retreated with lenalidomide.
- Subjects who do not tolerate 1 mg/kg/day will discontinue lenalidomide treatment.
- Subjects with non-hematologic toxicities that do not resolve to less than or equal to Grade 1 or baseline levels within 14 days will be off study treatment.
- Subjects with prolonged renal impairment (CLcr < 70 mL/min) lasting more than 14 days will be off study treatment.
- Subjects who do not demonstrate clinical benefit as per the Investigator at the end of Cycle 4 and beyond will be discontinued from lenalidomide treatment.

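### Four stop rules in Protocol 8.2 and 8.2.1 take subjects out of the study, although 6.23 sends everyone who permanently stops lenalidomide into follow-up

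*Protocol*

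**What the plan says.** Four treatment-stop rules use study-exit wording:

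- **Grade 3-4 GVHD** (Protocol 8.2.1): after permanent discontinuation of lenalidomide, subjects "will be managed at the discretion of the local HSCT physician. These subjects will be discontinued from the study".
- **Grade 1-2 GVHD** (8.2.1): after 14 days, subjects who need more than 0.5 mg/kg/day of corticosteroid or other systemic therapy "to manage the acute GVHD will be discontinued from the study".
- **Residual leukemia** (8.2.1, under the myelosuppression instructions): "If residual leukemia is demonstrated and the subject previously had achieved CR/CRi, the subject will be discontinued from the study".
- **Intolerance of the lowest dose** (8.2): "Subjects who do not tolerate the minimum dose level of 1 mg/kg/day (not exceeding 35 mg/day) will be discontinued from the study".

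Only the intolerance sentence is repeated elsewhere, in the Protocol Summary, Protocol 4.1 and SAP 4.1. The GVHD and residual-leukemia sentences stand in 8.2.1 alone.

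Protocol 6.23 has subjects enter the Follow-up Phase when they permanently stop drug. It allows three exits: death, withdrawn consent and loss to follow-up. It schedules a visit 28 days after the last dose, then contact every 3 months until 5 years after the last subject's first dose. The Summary, Protocol 4.1 and SAP 4.1 carry the same rule.

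**The concern.** None of the four triggers is among the exits that 6.23 allows, so the same subject is told both to leave the study and to enter follow-up. Section 12 gives the two kinds of stopping separate lists, treatment discontinuation in 12.1 and study discontinuation in 12.2, so a site can reasonably take study exit to mean what it says. Section 12.2 lists adverse events as a reason. It then asks for the treatment-discontinuation evaluations and an effort to obtain survival and AML-therapy information. It requires neither the 28-day visit nor the 3-monthly contacts.

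At stake is late, actively sought information in a group selected by outcome: GVHD, drug intolerance or relapse. SAP 11 reports drug-related SAEs over the whole study, including the 5-year follow-up, and SAP 10.2.5 counts transplants over the whole ITT population. Both analyses assume that follow-up continues.

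**Working it through.** The plan has no figure on this point to reproduce. The check compares passages.

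**1. The same events described elsewhere.**

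| Event | Study-exit wording | Treatment-stop wording |
|---|---|---|
| GVHD | 8.2.1, both grade groups | 1.4.2, which covers Grade 3 or greater in the same sentence: "lower grade GVHD that does not respond to protocol prescribed interventions (Section 8.2.1) will be off study treatment" |
| Intolerance of 1 mg/kg/day | 8.2, Summary, 4.1, SAP 4.1 | 8.2.1, dose reduction: "Subjects who do not tolerate 1 mg/kg/day (dose level -2) will discontinue lenalidomide administration"; 8.2.1, dose discontinuation: "Subjects who do not tolerate 1 mg/kg/day will discontinue lenalidomide treatment" |
| Residual leukemia after CR/CRi | 8.2.1 | none specific; 6.23 applies |

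Directly after the GVHD rules, 8.2.1 handles renal toxicity differently: "If toxicity does not resolve to eligibility by 14 days of dose interruption, then the subject will be off study treatment". A coordinator reading down the section sees what look like two distinct instructions.

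**2. Which was meant.** The evidence points to a treatment stop. Section 6.23 is general and has a closed list of exits. SAP 6 marks adverse event as not applicable when tabulating reasons for leaving the Follow-up Phase. The protocol also uses study loosely for study treatment. Table 2 (note i) times a pregnancy test at study discontinuation, where 6.8 puts it at the Treatment Discontinuation Visit. Section 8.2.1 calls a dosing delay a study interruption. Section 8.2 and Appendix L continue dosing until study-discontinuation criteria are met.

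**3. What a literal exit would lose.**

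| Item | Covered elsewhere? |
|---|---|
| AEs and SAEs to day 28 | Yes: Table 2, 6.21.1, 11.1, 11.5 |
| Day 28 pregnancy test (FCCBP/FCBP) | Yes: 6.8, 7.2 |
| Second primary malignancies, 5 years | Yes: 6.21.2, 6.25 |
| SAEs unresolved at exit | Yes: 11.2.6 |
| Survival and AML therapy | Yes, as a duty to make every attempt: 12.2 |
| Examination, hematology and chemistry at the 28-day visit | No |
| 3-monthly contacts on late drug-related SAEs, new therapy and HSCT | Only in part: late related SAEs must be recorded if the investigator learns of them (6.21.1, 11.1), and therapy falls under 12.2 |

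**4. Scale per affected subject.** Follow-up runs 60 months from the last subject's first dose, and accrual is expected to take about 40 months. The ceiling on contacts is 60/3 = 20 for the last subject enrolled and (40 + 60)/3 = 33.3, so 33, for the first. Time on treatment and death reduce this, and the documents give no survival figure for this population. For the transplant rate, one missed HSCT moves the ITT proportion by 1/43 = 2.3 percentage points at 43 subjects, or 1/18 = 5.6 points if the trial closed after Stage 1 with 18. A miss also requires the 12.2 effort to fail.

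**5. Number of subjects.** This cannot be derived. It would need the number enrolled after HSCT, the share of responders who meet the residual-leukemia rule, the frequency of persistent Grade 1-2 GVHD and of intolerance, and the share of sites reading the text literally. The documents give none of these.

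**The case against.** The strongest reply is that the documents resolve the conflict themselves. The Grade 3-4 GVHD rule first stops the drug permanently, which is exactly what triggers follow-up in 6.23, and the Summary and Protocol 4.4 also say that subjects are followed once lenalidomide is discontinued. In addition, 5-year follow-up for second malignancies requires continuing contact with the same subjects, which gives an occasion to hear of late SAEs, new therapy or transplant. On this view it is an editorial note.

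Much of that stands: the intent can be recovered and the likely loss is small. It does not remove the contradiction. The wording sits in operative rules that sites apply to individual subjects, and 12.2 supplies a category for acting on it. Contact about malignancies is also not the same as a scheduled question about drug-related SAEs.

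A reader might infer that these subjects lose all safety follow-up. They do not: the table above shows that AE and SAE recording to day 28, malignancies, unresolved SAEs and survival remain covered. A reader might also try to put a trial-level count on the loss. The GVHD threshold in 10.9.2 gives no upper bound, because crossing it only stops further post-HSCT enrollment and subjects already enrolled can still develop GVHD. The residual-leukemia rule stands within the myelosuppression instructions, so applying it to every relapsing responder may stretch it too far.

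**Conclusion.** The inconsistency is real and minor. The study-exit wording in the four rules is wrong by the protocol's own follow-up rule, by 1.4.2 for GVHD, by 8.2.1 itself for intolerance, and by SAP 6 for adverse events. The realistic exposure is the 3-monthly contacts and the examination and laboratory parts of the 28-day visit, in a subset selected by toxicity or relapse.

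Nothing supports reading this as a deliberate design choice, or as a threat to the trial's conclusions. The primary endpoint, the Stage 1 decision, the final decision rule and the GVHD stopping threshold do not depend on it. The conclusion rests on one assumption, that some site would follow the literal text. The documents leave that open but do not show how often it would happen.

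**What to change.** At all seven occurrences, replace the study-exit phrase with: permanently discontinued from lenalidomide and will enter the Follow-up Phase (Section 6.23). Six are in the protocol: the Summary, 4.1, 8.2, and three in 8.2.1 (residual leukemia, persistent Grade 1-2 GVHD, Grade 3-4 GVHD). One is in SAP 4.1.

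In 12.2, add that an adverse event leading to discontinuation of lenalidomide is not by itself a reason to leave the Follow-up Phase, in line with 6.23 and SAP 6. Residual leukemia is not an adverse event and could otherwise be entered under the open category in 12.2, so that rule depends on the rewording in 8.2.1.

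The cost is a wording change in the next protocol amendment and a matching edit to the SAP. No stopping trigger, visit or sample size changes, and the follow-up is already planned for every treated subject.

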The BMA slide (and/or bone marrow biopsy embedded paraffin slide) and peripheral blood smear from screening **must** be provided to the central reviewers at [REDACTED]. The central review [REDACTED] will provide standardized analysis and reporting for all subjects. The central reviewer's assessment will be used retrospectively to confirm diagnosis.

Creatinine clearance (CLcr) will be measured at screening using [Table 4](#) (see Section 7.2).

Treatment Phase

The lenalidomide dose will be calculated based on body weight. The starting dose will be 2 mg/kg/day with a maximum dose of 70 mg/day. Subjects enrolled in the study will receive lenalidomide for the first 21 days of each 28-day treatment cycle for up to a maximum of 12 cycles of study treatment. After the completion of 12 cycles of study treatment, subjects who demonstrate clinical benefit as per the Investigator may continue to receive lenalidomide in an OEP ([Appendix L](#)) until they meet the criteria for study discontinuation.

In the event of a specific protocol-defined toxicity, no more than 2 dose reductions will be allowed to doses of 1.4 mg/kg/day (not exceeding 50 mg/day) and 1 mg/kg/day (not exceeding 35 mg/day). The dose will not be re-escalated once it has been reduced ([Table 6](#)). Subjects who do not tolerate the minimum dose level of 1 mg/kg/day (not exceeding 35 mg/day) will be discontinued from the study. For additional details regarding dose reductions and dose capping see Section 8.2.1.

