6.14.2. Chemistry Laboratory Assessments

Serum chemistries including sodium, potassium, chloride, bicarbonate, calcium, phosphorus, blood urea nitrogen (BUN), creatinine, glucose, albumin, total protein, alkaline phosphatase, total bilirubin, direct bilirubin, aspartate aminotransferase (AST), alanine aminotransferase (ALT), and lactate dehydrogenase (LDH), and uric acid will be evaluated by the local laboratory at screening, on Days 1, 2, 4, 8, 15, and 22 of Cycle 1, on Days 1, 8, 15, and 22 of Cycle 2, on Day 1 of every cycle thereafter, at the Treatment Discontinuation Visit, on the 28-day Follow-up Visit, and at unscheduled visits (if clinically indicated). Serum chemistry laboratory values will not be collected on a laboratory CRF; instead, laboratory abnormalities that are considered AEs should be reported on the AE CRF (see Section 11).

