10. At least 4 weeks (from first dose) elapsed from donor lymphocyte infusion (DLI) without conditioning.

11. Subject has adequate renal function, which is defined as:

- Creatinine clearance calculated (Table 4) using the Schwartz formula, (Schwartz, 1976) or radioisotope glomerular filtration rate (GFR) > 70 mL/min/1.73 m².

Table 4: Creatinine Clearance Estimation using the Schwartz Formula

Age	Maximum Serum Creatinine (mg/dL)	
	Male	Female
1 month to < 6 months	0.4	0.4
6 months to < 1 year	0.5	0.5
1 to < 2 years	0.6	0.6
2 to < 6 years	0.8	0.8
6 to < 10 years	1.0	1.0
10 to < 13 years	1.2	1.2
13 to < 16 years	1.5	1.4
≥ 16 years	1.7	1.4

The threshold creatinine values in this table were derived from the Schwartz formula for estimating glomerular filtration rate (GFR) (Schwartz, 1976) utilizing child length and stature data published by the Center for Disease Control (CDC).

12. Subject has adequate liver function, which is defined as:

- Total bilirubin is ≤ 2 mg/dL unless the increase in bilirubin is attributable to Gilbert's Syndrome

- AST is ≤ 3.0 x upper normal limit (ULN) for age. For the purpose of this study, the ULN for AST is 50 U/L.
- ALT is ≤ 3.0 x upper normal limit (ULN) for age. For the purpose of this study, the ULN for ALT is 45 U/L.

13. Female Children of Childbearing Potential, Female of Childbearing Potential and male subjects that have reached puberty must agree to undergo physician-approved reproductive education and discuss the side effects of the study therapy on reproduction with parent(s) and/or guardian(s).
14. All subjects and/or parents/guardians must have an understanding that lenalidomide could have a potential teratogenic risk. Female Children of Childbearing Potential, defined as females who have achieved menarche and/or breast development in Tanner Stage 2 or greater and have not undergone a hysterectomy or bilateral oophorectomy and FCCBP defined as a sexually mature woman who has not undergone a hysterectomy or bilateral oophorectomy and has not been naturally postmenopausal for at least 24 consecutive months (ie, has had menses at any time in the preceding 24 consecutive months) must meet the following conditions below (Note: Amenorrhea following cancer therapy does not rule out childbearing potential):

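### The on-treatment renal hold, resume and stop limits are written as 70 mL/min, but the eligibility limit they refer to is 70 mL/min/1.73 m², and no on-treatment clearance method is stated

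*Protocol*

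**What the plan says.** Criterion 11 in Protocol Section 7.2 defines adequate renal function by the Schwartz formula, applied through Table 4, "or radioisotope glomerular filtration rate (GFR) > 70 mL/min/1.73 m²". Table 4 lists a maximum serum creatinine by age and sex.

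Section 8.2.1 sets three on-treatment rules, none of them indexed to body surface area:

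- **Hold** (Guidelines for Renal Insufficiency): "study treatment will be held for subjects who experience CLcr < 70 mL/min", to be confirmed by a second creatinine value within 3 days.
- **Resume at full dose** (same paragraph): "If CLcr returns to levels that meet initial eligibility criteria (> 70 mL/min) within 7 days of IP interruption". For subjects still impaired after 14 days, this paragraph refers only to eligibility, without a number.
- **Stop** (Dose Discontinuation list): "Subjects with prolonged renal impairment (CLcr < 70 mL/min) lasting more than 14 days will be off study treatment".

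On method, Section 4.1 and the Protocol Summary say "Creatinine clearance (CLcr) will be measured at screening using" Table 4. No method is given for later time points. Section 6.14.2 schedules serum creatinine throughout treatment, but "Serum chemistry laboratory values will not be collected on a laboratory CRF". Section 6.12 collects height only at screening and on Cycle 1 Day 1. The interruption criteria in SAP Section 9.7 cover skin rash and GVHD and contain no renal rule.

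**The concern.** The resume rule gives a number and calls it the eligibility criterion, but that number lacks the denominator the criterion carries. The two quantities agree only at a body surface area of 1.73 m². They are furthest apart in small children, and this trial enrols from age 1, with about half of subjects to be under 12.

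A site that took the unit at face value would err in both directions. A small child who had just met criterion 11 would fall under the hold rule and, if clearance stayed there, under the mandatory stop. That child would probably still count in the Response Rate population: anyone eligible and dosed, with a post-enrollment assessment or treatment failure, is included, and Appendix D classes failure to complete the first course as treatment failure. A large adolescent would be allowed a lower indexed clearance than at entry, on a drug that Section 8.2.1 describes as mainly cleared by the kidney.

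The missing method adds to the problem. Table 4 gives a creatinine ceiling, not a clearance that can be compared with 70.

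**Working it through.** The plan gives no figure to reproduce here, so the check is a comparison of the texts and a unit conversion.

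**Texts side by side**

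| Rule | Section | Limit as written | Tied to eligibility? |
|---|---|---|---|
| Entry | 7.2, criterion 11 | > 70 mL/min/1.73 m² | – |
| Hold | 8.2.1, Renal Insufficiency | < 70 mL/min | By context only |
| Resume | 8.2.1, Renal Insufficiency | > 70 mL/min | Yes, in words |
| Stop after 14 days | 8.2.1, Renal Insufficiency | No number | Yes, in words |
| Stop after 14 days | 8.2.1, Dose Discontinuation | < 70 mL/min | No |

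The denominator is missing in all three places where a number appears on treatment, so no neighbouring statement of the number corrects it.

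**Inputs.** The 70 and the 1.73 m² come from the protocol. The body surface areas and the normal indexed GFR values are assumptions chosen to show the range; the documents give neither.

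**Step 1: what an absolute 70 mL/min means on the indexed scale.**
Indexed equivalent = 70 × 1.73 / BSA = 121.1 / BSA.

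| Assumed BSA (m²) | Calculation | Indexed equivalent (mL/min/1.73 m²) | Entry limit |
|---|---|---|---|
| 0.5 | 121.1 / 0.5 | 242 | 70 |
| 0.8 | 121.1 / 0.8 | 151 | 70 |
| 1.0 | 121.1 / 1.0 | 121 | 70 |
| 1.73 | 121.1 / 1.73 | 70 | 70 |
| 2.0 | 121.1 / 2.0 | 60.6 | 70 |

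**Step 2: how small a child with normal function must be to fall below 70 mL/min.**
Break-even BSA = 70 × 1.73 / indexed GFR.

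- Indexed GFR 90: 121.1 / 90 = 1.35 m²
- Indexed GFR 120: 121.1 / 120 = 1.01 m²
- Indexed GFR 150: 121.1 / 150 = 0.81 m²

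Below these sizes, a child with normal indexed function meets the literal hold rule from the first day of treatment.

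**Step 3: the limit that was probably meant, in absolute terms.**
70 × BSA / 1.73 gives 70 × 0.5 / 1.73 = 20.2 mL/min at 0.5 m², 32.4 at 0.8 m² and 40.5 at 1.0 m². For small children the literal limit is therefore about two to three and a half times the intended one (70 / 32.4 = 2.2; 70 / 20.2 = 3.5).

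**The case against.** The best reply is that the text largely resolves the ambiguity itself. The resume rule defines its level by reference to eligibility, and the 14-day sentence in the same paragraph asks only whether the subject has returned to eligibility. A child who satisfies criterion 11 cannot fail that test, so the absolute reading contradicts the paragraph it comes from. The Dose Discontinuation bullet can be read as a summary of that rule. Table 4 is the only clearance method in the protocol, and the confirmatory test is a repeat creatinine, which fits a creatinine ceiling. No urine collection, absolute-clearance formula or on-treatment height is scheduled, so a site would have to bring its own method to reach the harmful reading. A child who met the hold rule at baseline, just after the sponsor had verified eligibility, would also prompt a query.

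A related reply concerns detection. Although chemistry values are not on a laboratory CRF, a laboratory abnormality that leads to dose interruption is an adverse event (Section 11.3), dose interruptions are recorded (Section 6.16), and entries are checked against source (Section 16.1).

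Much of this stands. The indexed value is the likely intent, widespread wrongful removal is not to be expected, and a hold would leave a trace. Only the narrower point on detection remains: the collected laboratory data would not show which reading led to the hold. What the reply does not supply is an instruction. The discontinuation bullet is mandatory, gives the unindexed figure and makes no reference to eligibility, and nothing carries the screening method into the treatment phase.

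**Conclusion.** The concern holds. The three numerical limits in Section 8.2.1 are wrong as written: they omit the /1.73 m² of the criterion they are meant to restate, and the on-treatment method is left to inference.

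The size is conditional. If sites use Table 4 on treatment, there is no discrepancy. If a site reads the limit as absolute, it is an indexed 242, 151 or 121 mL/min/1.73 m² at assumed body surface areas of 0.5, 0.8 and 1.0 m², against 70 at entry. At an assumed 2.0 m² it is slightly looser than entry, at 60.6. With an assumed indexed GFR of 90 to 150, children below 1.35 to 0.81 m² would meet the hold rule despite normal function.

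The two-stage boundaries (3 of 18, 8 of 43) and the planned analyses are not affected. The issue is dosing safety and consistency, with a secondary risk that a wrongly stopped child is counted as a non-responder. The mismatch itself is certain; how often it would matter in practice cannot be judged from the documents. It should be corrected.

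**What to change.** In Section 8.2.1, write 70 mL/min/1.73 m² at three places: the hold statement and the resume statement under Guidelines for Renal Insufficiency, and the renal bullet under Dose Discontinuation.

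Add one sentence saying that renal function on treatment is assessed as in criterion 11, by Schwartz through Table 4 or by indexed radioisotope GFR. With Table 4, a hold means serum creatinine above the ceiling for the subject's age and sex. That needs only creatinine, age and sex, all already available, so no new assessment is required. If a height-based Schwartz calculation is preferred, height must also be collected after Cycle 1 Day 1.

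The cost is a wording clarification, with no change to sample size, endpoints or SAP analyses.
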